7.2 Subjective ocular symptoms throughout the day

Subjective ocular symptoms throughout the day (irritation/burning, stinging, itching, tearing, eye dryness feeling, foreign body sensation) will be assessed using a 4-point ordinal scale from 0 to 3, 0 indicating no symptom and 3 indicating very disturbing symptom.

Frequency distribution of each symptom will be presented at screening, baseline (Day 1), Week 6 and Week 12. Comparison between treatment groups will be performed for each symptom at Week 6 and at Week 12 using a CMH test with modified ridit scores stratified by country.

The total score of the 6 symptoms, ranging from 0 to 18, will be calculated and presented for screening, baseline (Day 1), Week 6 and Week 12. Change in total score from baseline will also be described at Week 6 and Week 12. Comparison of the change from baseline in total score between treatment groups will be performed at Week 6 and Week 12 using an MMRM model. The model will include as fixed factors, treatment, scheduled visit time point (Week 6 and Week 12), baseline, wash-out duration and country, treatment by visit interaction and patient as random factor.

Data relative to other symptoms will be provided in individual data listing. Other symptoms will be coded using MedDRA dictionary version the most recent possible at the database lock.

Note: If the patient did not feel any ocular symptom throughout the day, each symptom will be scored 0.

7.3 Subjective ocular symptoms upon instillation

Subjective ocular symptoms upon instillation (irritation/burning, stinging, itching, tearing, eye dryness feeling, foreign body sensation) will be assessed using a 4-point ordinal scale from 0 to 3, 0 indicating no symptom and 3 indicating very disturbing symptom.

Frequency distribution of each symptom will be presented at Week 6 and Week 12. Comparison of each symptom between treatment groups, separately for Week 6 and Week 12 will be performed using a CMH test with modified ridit scores stratified by country.

The total score of the 6 symptoms, ranging from 0 to 18, will be calculated and presented for Week 6 and Week 12.

Comparison of the total score between treatment will be performed at Week 6 and Week 12 using an MMRM model. The model will include as fixed factors, treatment, scheduled visit time point (Week 6 and Week 12), country, wash-out duration treatment by visit interaction and patient as random factor.

Data relative to other symptoms will be provided in individual data listing. Other symptoms will be coded using MedDRA dictionary version the most recent possible at the database lock.

Note: If the patient did not feel any ocular symptom upon instillation, each symptom will be scored 0.

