PROTOCOL SYNOPSIS

Title	Efficacy and safety assessment of T4032 (unpreserved bimatoprost 0.01%) versus Lumigan® 0.01% in ocular hypertensive or glaucomatous patients.
Sponsor	Laboratoires THÉA
EudraCT-Number	2017-000846-23
Sponsor Study No.	LT4032-301
International Coordinator	
Study Centres	This international study is planned to be carried out at approximately 130 sites spread over 15 to 25 countries.
Planned Schedule	Planned initiation: October 2018 Planned last patient last visit: December 2020
Study Phase	Phase III
Primary Study Objective	To demonstrate the non-inferiority of T4032 unpreserved eye drops compared to Lumigan® 0.01% in terms of efficacy.
Secondary Study Objective(s)	To evaluate the safety and efficacy of T4032 versus Lumigan® 0.01%.
Sample Size	360 evaluable patients Accounting for a 10% drop-out/non evaluable rate, 400 initially treated patients are expected to be randomised. Number of screened patients will depend on the screen failure rate and is estimated at 668 patients.
Study Design	International, multicentre, randomised, 2 parallel groups, investigator-masked, 3-month treatment. 4 visits: 
• Visit #1: Day -49 ± 3 days (Screening Visit)• Visit #2: Day 1 (Randomisation Visit)• Visit #3: Week 6 (Day 42 ± 3 days)• Visit #4: Week 12 (Day 84 ± 7 days) (Final visit)• Follow-up phone call: Week 16 (Day 112 ± 7 days) Run-In/Wash-Out: Patient must be willing to discontinue her/his current treatment for 7 weeks ($49 \text{ days} \pm 3$ days) prior to the randomisation visit, in order to determine the IOP eligibility. Patient must follow a run-in period with only brinzolamide eye drops (Azopt®), one drop in each eye twice a day (morning and evening) for 5 weeks.

	The Azopt® treatment must be stopped for 2 weeks prior to the randomisation visit.
Study Duration	23 weeks total of study duration: 5 weeks of run-in + 2 weeks of wash-out 12 weeks of treatment duration 4 weeks of follow-up.

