All the ocular assessments have to be performed in both eyes.

- (1) Ocular symptoms (irritation/burning, stinging, itching, tearing, eye dryness feeling, foreign body sensation), scored using 0-3 scale, will be collected by the investigator /delegate.
- (2) At Screening Visit, one IOP measurement should be performed at 08:00 (\pm 30 minutes). At Day 1, Day 42/Week 6 and Day 84/Week 12, IOP should be measured at three time points: 08:00, 10:00 and 16:00 (each \pm 30 minutes) with a.m. measurements of IOP at least 2 hours apart. IOP measurements should be done at the same hours (\pm 30 min) than Day 1, by the same investigator and using the same technique (Goldmann applanation tonometer) for all visits.
- (3) To be performed if fundus examination / central corneal thickness measurement / automated visual field not done within the previous 12 months and/or results dating from the last 12 months not available.
- (4) To be performed only if the IOP is not stable at the Week 12 visit or if the ophthalmologist judges that it is necessary.
- (5) Azopt® must be stopped for 2 weeks before the Randomisation Visit.
- (6) Slit lamp examination: Score of each ocular sign (blepharitis, eyelid oedema, iris pigmentation modification, abnormal eyelashes aspect, folliculo-papillary conjunctivitis or other ocular abnormality) will be recorded in each eye using 0-3 scale.
- (7) Urinary test to be done for childbearing potential women.
- (8) Run-in treatment (Azopt®) will be instilled by the patient one drop in each eye twice a day (morning and evening) for 5 weeks.
- (9) One drop of IP (T4032 or Lumigan®) will be instilled by the patient in each eye once daily at 20:00 (\pm 1 hour) for 12 weeks.
- (10) Efficacy and ocular tolerance will be assessed by the investigator and the patient as very satisfactory, satisfactory, not very satisfactory, or unsatisfactory.
- (11) In case of AE, all treatments of the follow-up period will be collected.

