3.5 Other strata and covariates

Country, wash-out duration factor and possible impact of COVID-19 pandemic will be included in all models as covariate, and CMH test used for ordered qualitative variables will be stratified by country.

Baseline value will be included in all MMRM and ANCOVA as covariate:

- For analyses on the change from baseline in IOP, baseline IOP will be included as covariate in MMRM and ANCOVA
- For analysis on the change from baseline in total symptoms score throughout the day, corresponding baseline value will be included as covariate in MMRM

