4.3.2 Baseline

Baseline will be defined for each assessment as an evaluation before the first instillation of the IMP:

- For IOP, the value recorded at 08:00 at Day 1, respectively at 10:00 and at 16:00, will be the baseline for analysis of IOP at 08:00, respectively at 10:00 and at 16:00
- For visual field, fundoscopy and corneal thickness, the value recorded at screening visit will be the baseline
- For others parameters, the value recorded at Day 1, will be the baseline for analysis

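### The MMRM for the upon-instillation symptom total (SAP 7.3) leaves out an available Day 1 prognostic covariate, and the baseline rule in SAP 3.5 does not fit this model

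*SAP*

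**What the plan says.** SAP 7.3 analyses the total of six symptoms upon instillation at Week 6 and Week 12. The response is the score itself, not a change from baseline. The model is: "The model will include as fixed factors, treatment, scheduled visit time point (Week 6 and Week 12), country, wash-out duration treatment by visit interaction", with patient as the random factor. The Table 5.10 shell matches this. Its rows are treatment, visit, wash-out duration, country and treatment by visit, with nothing for a baseline.

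SAP 3.5 opens with a general rule: "Baseline value will be included in all MMRM and ANCOVA as covariate". Two cases follow. One is IOP: "For analyses on the change from baseline in IOP, baseline IOP will be included as covariate in MMRM and ANCOVA". The other is the daytime symptom score: "For analysis on the change from baseline in total symptoms score throughout the day, corresponding baseline value will be included as covariate in MMRM". The upon-instillation total is not named.

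SAP 7.2 handles the companion score, the same six symptoms felt throughout the day. That total "will be calculated and presented for screening, baseline (Day 1), Week 6 and Week 12", its model includes the baseline, and Table 5.7 has a row for it.

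SAP 4.3.2 sets the condition for any baseline: "Baseline will be defined for each assessment as an evaluation before the first instillation of the IMP".

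**The concern.** Read literally, the opening of 3.5 covers the 7.3 model, which is an MMRM, yet 7.3 and Table 5.10 contain no baseline term. A programmer who starts from 3.5 will look for a value that 7.3 does not provide.

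The second matter is precision. Patients may differ in how readily they report ocular discomfort. Whatever part of that difference is stable and is not explained by country or wash-out stays in the between-patient variance of the 7.3 comparison. The unstructured covariance links Week 6 and Week 12 within a patient, but it does not remove this variation from the contrast between arms. A pre-treatment covariate can remove some of it, and it does not have to be the same measure as the outcome. It needs only to precede treatment and to predict the outcome. What is at stake is the width of the interval for a listed safety endpoint in a comparison of an unpreserved with a preserved bimatoprost drop.

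**Working it through.** **Is there an own baseline for this score?** SAP 4.3.2 requires a baseline to precede the first study drop. The study drop "will be instilled by the patient in each eye once daily at 20:00", whereas the Day 1 IOP readings are at 08:00, 10:00 and 16:00. The run-in drop is no longer in use by then. The Protocol synopsis says "The Azopt® treatment must be stopped for 2 weeks prior to the randomisation visit"; SAP 1.4.1 gives two weeks or one week according to the protocol amendment, and either puts the last run-in drop before Day 1. So there is no reaction to the study drop to score at that visit. SAP 7.3 and Tables 5.8 to 5.10 accordingly show this score at Week 6 and Week 12 only. The visit marks for the upon-instillation row of the schedule are incomplete in the text available to me, so the timing rests on 7.3 and these tables.

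**Is there a usable substitute covariate?** The two totals compare as follows.

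| | Throughout the day (4.3.14, 7.2) | Upon instillation (4.3.15, 7.3) |
|---|---|---|
| Symptoms | six | the same six |
| Item scale, total | 0 to 3, 0 to 18 | 0 to 3, 0 to 18 |
| Day 1 value | yes | none |
| Response in the MMRM | change from baseline | score itself |
| Baseline in the model | yes | no |

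The Day 1 throughout-the-day total is pre-treatment, has the same item structure and is already derived. It is a different construct, so it is a prognostic covariate and not a baseline of the 7.3 endpoint.

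**The plan's own figures.** None concerns this score. The only stated design figure is for IOP (SAP 1.5: margin 1.5 mmHg, SD 3 mmHg, 180 per arm, correlation 0.7). It reproduces: SE = 3 × √(2/180) = 0.316; 1.5/0.316 − 1.96 = 2.78; power is 99.7% per time point and 99.3% jointly over the three, consistent with the stated figure of over 90%. Also 360/0.9 = 400. None of this informs the symptom score, for which no SD, effect size or correlation is given.

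**Size of the possible gain.** Let r be the partial correlation between the Day 1 throughout-the-day total and the on-treatment instillation total, given country and wash-out duration, which are already in the model. Then approximately:

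- residual variance is multiplied by 1 − r²
- interval width is multiplied by √(1 − r²)
- the equivalent sample-size factor is 1/(1 − r²)

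| Assumed r | Variance reduction | Interval narrower by | 360 patients equivalent to |
|---|---|---|---|
| 0 | 0% | 0% | 360 |
| 0.1 | 1% | 0.5% | 364 |
| 0.2 | 4% | 2.0% | 375 |
| 0.3 | 9% | 4.6% | 396 |
| 0.4 | 16% | 8.3% | 429 |
| 0.5 | 25% | 13.4% | 480 |

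Every r here is an assumption.

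**The case against.** The strongest reply is that nothing has been left out. The score has no baseline under 4.3.2. The two cases listed in 3.5 are both change-from-baseline analyses, which 7.3 is not. Text and shells agree for each endpoint: Table 5.7 has a baseline row where 7.2 has the term, and Table 5.10 has none where 7.3 has none. All of this stands. A reader might infer that 7.3 breaches 3.5, or that a collected baseline is being discarded. The documents support neither; they show only that the opening sentence of 3.5 is wider than its list.

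It can also be said that daytime symptoms after the run-in drop has stopped are not the reaction to a drop, and that no section states that they predict it. That stands as well, and it is why the correlation must be treated as unknown and may be weak.

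A reader might further infer that a chance Day 1 imbalance passes whole into the treatment difference. It does not. It carries through only as far as the Day 1 score predicts the outcome, and the unadjusted interval already allows for chance imbalance.

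Finally, this is a safety endpoint with no success criterion or power claim, and SAP 7.3 also compares each symptom by a CMH test stratified by country. That limits the importance of the point. It does not remove it, since a covariate need not be the endpoint's own baseline to be worth including.

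**Conclusion.** The point holds as a minor one about precision and wording. The 7.3 model has no pre-treatment symptom covariate, a reasonable candidate is already derived, and the general sentence in 3.5 does not fit this model. The comparison as planned is unbiased.

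The gain depends on a partial correlation that the documents do not give: about 0.5% to 13% off the interval width for r of 0.1 to 0.5, and nothing when r is near 0. To describe this as certain precision obtained at no cost would go too far, because both the gain and the number of patients lost to a missing Day 1 total are unknown.

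**What to change.** - Add the Day 1 total of symptoms throughout the day as a covariate in the 7.3 MMRM, with a matching row in Table 5.10. Call it a prognostic covariate, not the baseline of this endpoint, so that it does not conflict with 4.3.2.
- Reword 3.5 so that adjustment for an endpoint's own baseline applies where one exists, and state there that the upon-instillation model uses the Day 1 throughout-the-day total instead. If the sponsor declines the covariate, 3.5 should still name this model as an exception.

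The change should be fixed before the randomisation list is opened. It costs one model term, one shell row and a sentence in 3.5, and needs no new data. The drawback is that a patient with a missing Day 1 total leaves this model, and under 4.3.14 a single missing item makes that total missing. Such patients should be rare, but the documents give no count, so the number excluded should be reported.

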7.4 Ocular signs – Slit lamp examination

Each ocular sign (blepharitis, eyelid oedema, iris hyperpigmentation, abnormal eyelashes aspect, folliculo-papillary conjunctivitis) assessed for each eye on a 4-point ordinal scale from 0 to 3, 0 indicating absence and 3 indicating severe sign.

Frequency distribution of each ocular sign will be presented at screening, baseline (Day 1), Week 6 and Week 12, on the worse eye and the contralateral eye. Comparison between treatment groups will be performed for each ocular sign, at Week 6 and at Week 12, using a CMH test with modified ridit scores stratified by country, separately for the worse eye and for the contralateral eye.

Data relative to other ocular abnormalities will be provided in individual data listing. Other ocular abnormalities will be coded using MedDRA dictionary version the most recent possible at the database lock.

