Investigational Product(s) (IP)	Run-in product: Azopt® Preserved brinzolamide 10mg/mL eye drops presented in multidose container. Route of administration: In the conjunctival cul-de-sac of each eye. Daily dose regimen: 1 drop in each eye twice a day, morning and evening during 5 weeks. Test product: T4032 Unpreserved bimatoprost 0.01% eye drops presented in unit dose (UD). Comparator product: Lumigan® 0.01% Preserved bimatoprost 0.01% eye drops presented in multidose container. Route of administration: In the conjunctival cul-de-sac of each eye. Daily dose regimen: 1 drop in each eye once daily at 20:00 (\pm 1 hour) from Day 1 to Week 12.
Inclusion Criteria	
At Screening Visit (D-49):
 
1.1 Informed consent signed and dated. 1.2 Patient aged \geq18 years old. 1.3 Both eyes with $500 \mu\text{m} \leq$ central corneal thickness $\leq 600 \mu\text{m}$. 1.4 Both eyes with diagnosed open-angle glaucoma or ocular hypertension, initially treated and controlled (including IOP $\leq 18 \text{ mmHg}$) for at least 6 months by any prostaglandin monotherapy. 1.5 Both eyes with IOP $\leq 18 \text{ mmHg}$.
 
At Randomisation Visit (D1) at 8:00:
 
1.6 Both eyes with $22 \text{ mmHg} \leq \text{IOP} < 34 \text{ mmHg}$ and with asymmetry between eyes $\leq 3 \text{ mmHg}$.

Exclusion Criteria	
Ophthalmic Exclusion Criteria in AT LEAST ONE EYE [2.1]
 
2.1.1 Fundus examination not performed or not available within 12 months. 2.1.2 Visual field not performed or not available within 12 months. 2.1.3 Significant worsening according to the two last visual fields (at least 6 months between the two visual fields). 2.1.4 Advance stage of glaucoma, defined by at least one of the following criteria:

	
2.1.4.1 Absolute defect in the ten degrees central point of the visual field.
 
2.1.4.2 Severe visual field loss: MD < -18 dB.
 
2.1.4.3 Risk of visual field worsening as a consequence of participation in the study according to the investigator's best judgement.

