7.1 Conjunctival hyperaemia – Slit lamp examination

Conjunctival hyperaemia assessed for each eye using the McMonnies photographic 6-point ordinal scale from 0 to 5 will be presented by frequency distribution at each assessment time (screening, baseline [Day 1], Week 6 and Week 12), for the worse eye and contralateral eye. Comparison between treatment groups will be performed at Week 6 and at Week 12, using a CMH test with modified ridit scores stratified by country, separately for the worse eye and for the contralateral eye.

In addition, frequency distribution of change from baseline will be presented for conjunctival hyperaemia at Week 6 and Week 12 for the worse eye and contralateral eye. The following categories will be defined and presented: i) improvement (*i.e.*, decrease of symptom score from baseline), absence stable, presence stable, worsening (*i.e.*, increase of symptom score from baseline), ii) improvement, no change, worsening, iii) improvement of more than 1 point (*i.e.*, change from baseline <-1 , no significant change (*i.e.*, change from baseline ≥-1 and ≤ 1), worsening of more than 1 point (*i.e.*, change from baseline >1). Comparison of changes from baseline in 3 classes (improvement, no change, worsening) for conjunctival hyperaemia between treatment groups will be performed at Week 6 and Week 12, using a CMH test with modified ridit scores stratified by country, separately for the worse eye and for the contralateral eye.

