7.5 Corneal staining according to Oxford grading scheme

The Oxford 0-5 grading scheme assesses the staining of the corneal area.

The CFS score (ranging from 0 to 5) will be calculated and frequency distribution will be presented at screening, baseline (Day 1), Week 6 and Week 12, for the worse eye and for the contralateral eye. Comparison of the CFS score between treatment groups will be performed at Week 6 and at Week 12 using a CMH test with modified ridit scores stratified by country, separately for the worse eye and for the contralateral eye.

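### The between-arm tests of ocular signs, corneal staining and single daytime symptoms leave out the Day 1 grade already collected, which can cost power and leaves new or worsened findings untabulated

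*SAP*

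**What the plan says.** Three groups of ocular safety endpoints are compared between arms on the grade recorded at the visit:

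- **Ocular signs (SAP 7.4):** "Comparison between treatment groups will be performed for each ocular sign, at Week 6 and at Week 12, using a CMH test".
- **Oxford staining (SAP 7.5):** "Comparison of the CFS score between treatment groups will be performed at Week 6 and at Week 12 using a CMH test".
- **Each symptom throughout the day (SAP 7.2):** "Comparison between treatment groups will be performed for each symptom at Week 6 and at Week 12 using a CMH test".

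Stratification is set in SAP 3.5: "CMH test used for ordered qualitative variables will be stratified by country". The baseline-covariate rule in the same section covers MMRM and ANCOVA, not CMH. Screening and Day 1 distributions are tabulated by arm (Tables 5.5 and 5.11 to 5.14), but they do not enter the tests, and these shells have no change rows.

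Elsewhere the SAP does use baseline. For hyperaemia (7.1): "Comparison of changes from baseline in 3 classes (improvement, no change, worsening) for conjunctival hyperaemia between treatment groups will be performed", with Table 5.2 as its shell. The daytime symptom total is analysed as change from baseline in an MMRM that includes the baseline value (7.2). SAP 4.3.11 defines change classes, which are applied only to hyperaemia.

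Symptoms upon instillation (7.3) are a separate case: "Frequency distribution of each symptom will be presented at Week 6 and Week 12". No Day 1 value is used for them, so this point does not cover them.

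On entry, patients have been treated "for at least 6 months by any prostaglandin monotherapy" (Protocol, inclusion criterion 1.4). They then take preserved brinzolamide for 5 weeks and have a wash-out, which is 2 weeks in the current protocol. SAP 1.4.1 and 4.3.8 give the wash-out lengths before and after amendment 1 in opposite order, which should be reconciled separately.

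**The concern.** A grade present on Day 1 cannot have been caused by T4032 or Lumigan. The entry criteria exclude only the top grades of blepharitis (3) and Oxford staining (4 and 5), so milder findings from earlier treatment are eligible. If many patients carry such a finding and it persists similarly in both arms, it adds variance to the visit-grade comparison and no information about the randomised products.

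Two things are at stake under the secondary objective of evaluating safety. The first is power to see a real difference in findings that arise on treatment. The second does not depend on power: separate Day 1, Week 6 and Week 12 distributions cannot show how many patients developed, worsened, kept or lost a finding, and no planned summary of these graded scales shows it.

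**Working it through.** **The plan's own figure.** The only stated design figures concern IOP. With 180 per arm, SD 3 and margin 1.5, the standard error is 3 × √(2/180) = 0.316. Power per time point is Φ(1.5/0.316 − 1.96) = Φ(2.78) = 99.7%. Jointly over three time points with correlation 0.7 it is 99.3%, which agrees with more than 90%. The enrolment figure also reproduces: 360/0.90 = 400. No figure is stated for the safety comparisons, so what follows is illustration.

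**Inputs.** From the documents: 485 randomised 1:1, about 242 per arm, and a two-sided 5% test. Assumed: a present/absent finding, Day 1 prevalence b, share s of Day 1 findings still present at the visit, and new onset of 15% versus 7% among patients free of the finding on Day 1.

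**Formulas, equal persistence in both arms.**
- Visit rate per arm = b·s + (1 − b)·onset. The level test is the usual two-proportion test on these rates.
- Test stratified by Day 1 status: difference d = (1 − b)(0.15 − 0.07); variance v = (2/242)·[b·s(1 − s) + (1 − b)·0.11·0.89]; power = Φ(d/√v − 1.96).

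Example with b = 20%, s = 100%: the visit rates are 32.0% and 25.6%, and the level test has 34% power. For the stratified test d = 0.064 and √v = 0.0254, so power = Φ(2.52 − 1.96) = 71%.

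| Day 1 prevalence | Level, s = 100% | Day 1 stratum, s = 100% | Level, s = 60% | Day 1 stratum, s = 60% |
|---|---|---|---|---|
| 0% | 80% | 80% | 80% | 80% |
| 10% | 51% | 76% | 58% | 66% |
| 20% | 34% | 71% | 41% | 51% |
| 30% | 24% | 65% | 29% | 38% |
| 40% | 18% | 59% | 21% | 27% |

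**Unequal persistence.** If 80% of Day 1 findings persist in one arm and 50% in the other, in the same direction as new onset, the level test has 86% to 98% power over 10% to 40% prevalence. The Day 1 stratum gives 92% to 99.8%. Counting new onset alone gives only 76% to 59%, because it ignores resolution.

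**Is plain change from Day 1 a better test?** Take a score for which the level test has 80% power. Then power = Φ(2.80/√f − 1.96), with f = 1 for level, 2(1 − r) for change and 1 − r² for baseline adjustment, where r is the correlation between Day 1 and the visit.

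| r | Level | Plain change | Baseline-adjusted |
|---|---|---|---|
| 0 | 80% | 51% | 80% |
| 0.3 | 80% | 66% | 84% |
| 0.5 | 80% | 80% | 90% |
| 0.7 | 80% | 95% | 97.5% |

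**Simulation with country strata** (240 per arm, 30% Day 1 prevalence, new onset 10% versus 4%). The level test against the Day 1 stratum gave 15% versus 56% at full persistence, 20% versus 30% at 60%, and 22% versus 26% at 40%. At 40% persistence the plain change test gave 14%. Adding the Day 1 stratum kept the 5% error rate. These figures can move by a few points with the number and size of countries assumed.

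**The case against.** The strongest reply is that nothing here is invalid. Randomisation makes the visit-grade comparison unbiased, and the 5% level already allows for chance imbalance on Day 1, which would also be visible in the by-arm tables. That stands. A reader might infer that Day 1 findings bias the result or make the p-value wrong; the design does not support that.

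A reader might also infer that dilution is certain. It is not. It needs a material Day 1 prevalence that persists, and the documents give neither rate. Patients are about 7 weeks off prostaglandin by Day 1 under the current protocol and have a wash-out from brinzolamide. Full persistence is more plausible for iris pigmentation than for burning, tearing or eyelid oedema. If findings resolve more in one arm, the level test captures that.

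A third tempting step is to make change from Day 1 the main comparison, as 7.1 does for hyperaemia. The calculations do not support it: plain change loses to level when r is below 0.5, or below about 60% persistence in the simulated case.

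The SAP also follows the protocol, which names change from baseline only for hyperaemia and lists the others as scores, so this is no departure. Ocular TEAEs by arm cover part of the gap. They depend on what the investigator reports as an event, however, and do not replace a count of change on the graded scales.

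**Conclusion.** The point holds in a limited form. For signs, Oxford staining and each daytime symptom, the plan collects a Day 1 grade and leaves it out of the between-arm test. The comparison remains unbiased; the loss is in power and in what the tables can show.

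The size depends on assumed rates. With new onset of 15% versus 7% and Day 1 prevalence of 10% to 40%, the level test has 51% to 18% power under full persistence, against 76% to 59% with a Day 1 stratum. At 60% persistence the gain is smaller: 58% to 21% against 66% to 27%. With no Day 1 findings there is nothing to gain. In the calculated scenarios with Day 1 findings, the Day 1 stratum did better than the level test, while plain change did not do so consistently.

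These are secondary safety comparisons with no decision rule, so this is a cheap improvement and not a validity fault.

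**What to change.** Before the randomisation list is opened, amend SAP 7.2 (single symptoms), 7.4 and 7.5 as follows:

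1. Keep the Week 6 and Week 12 grade as the tested outcome, using the CMH test with modified ridit scores, and add the Day 1 grade as a stratum alongside country.
2. State in advance when the Day 1 grade is collapsed, for example to absent/present. The Table 1.4 shell lists 17 countries; the pooling in 4.3.1 reduces three of these to one group, leaving 15. Two Day 1 classes then give 30 strata, about 16 patients each (485/30). Four classes give 60 strata, about 8 each.
3. Add tables by arm of change from Day 1 in the 4.3.11 classes, re-using the Table 5.2 shell, so that new or worsened findings can be read directly. Keep these supportive; do not make plain change the main test.
4. Leave 7.3 unchanged.

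The cost is SAP wording and extra safety tables, with no new data. Some strata will be sparse and contribute little, and patients without a Day 1 grade drop out of the adjusted test, so their number should be reported.
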